4.4.7. Treatment Compliance

All subjects were to receive two doses of study product in the clinic. The first dose is administered at Visit 1 (Day 0) and the second dose is administered at Visit 6 (Day 56). The number of doses of study product administered to subjects will be presented by treatment group as part of the subject disposition table ([Table 3](#)). The listing of subjects excluded from the primary efficacy analysis will present subjects who received less than 2 doses ([Listing 1](#)). A listing of number of vaccinations received and missed for all subjects is provided in [Listing 8](#).

4.5. Efficacy, Immunogenicity, and Safety Variables

See Section 3.3 for efficacy and immunogenicity variable definitions.

The safety variables to be assessed are reactogenicity events, unsolicited adverse events (AEs), serious adverse events (SAEs), and protocol specified clinical safety laboratory, physical exam, and vital sign parameters.

Subjects were to record temperature and the presence and intensity of post-vaccination reactogenicity events daily on an 8-day subject memory aid. Local solicited reactogenicity events include: pain, tenderness, erythema, induration and warmth at the injection site. Systemic solicited reactogenicity events include: fever, chills, arthralgia/joint pain, malaise/fatigue, myalgia/body aches, headache, nausea, vomiting, abdominal pain. Erythema and induration at the vaccination site will be measured in millimeters and functional grade. Any symptoms still present at Day 7 will continue to be followed until symptom resolution.

Solicited reactogenicity symptoms will be graded using the scale in section 9.4.4 of the protocol.

Unsolicited adverse event severity will be graded according to parameters shown in Appendix B of the protocol or if graded differently this will be noted in the tables using the definitions in section 9.4.2 of the protocol.

Clinical laboratory evaluations for safety will be performed by local (clinical) laboratories. Venous blood samples will be collected from each subject prior to each vaccination and according to the Study Schedule in Appendix C of the protocol. Clinical safety lab parameters to be followed include WBC, HgB, platelets, ALT, and creatinine. Urine will be collected to evaluate glucose and protein, which will be performed at screening only. Toxicity grades for each clinical laboratory parameter can be found in Appendix B of the protocol.

Multiple observations within a specific visit period are accepted. In the case of multiple observations within a specific window, the assessment value that is closest to the scheduled visit will be used in the analyses for the post-baseline records. For screening and baseline visits, the last assessment value prior to first vaccination will be used as the baseline measurement. All the recorded data will be listed. If observations have the same distance to the scheduled assessment, the latest one will be used.

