9.4.2 Assessment of Severity

Event severity will be graded according to parameters shown in Appendix B or if not, noted in the tables using the definitions below:

- 1 = Mild (awareness of a symptom but the symptom is easily tolerated; the symptom requires minimal or no treatment)
- 2 = Moderate (discomfort enough to cause interference with usual activity)
- 3 = Severe (incapacitating; unable to perform usual activities; requires absenteeism/bed rest)
- 4 = Life-threatening
- 5 = Death

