9.4.4 Assessment of Reactogenicity

Subjects will be asked to record events daily on an 8-day subject memory aid. The subject will record temperature and the presence and intensity of post-vaccination reactogenicity events, including pain, tenderness, erythema, induration and warmth at the at injection site; fever, chills, arthralgia/joint pain, malaise/fatigue, myalgia/body aches, headache, nausea, vomiting, abdominal pain and any other symptoms they might be experiencing after vaccination. Erythema and induration at the vaccination site will be measured in millimeters. Any symptoms still present at Day 8 will continue to be followed until symptom resolution. Subjects will also be asked to record any medications taken and any emergency room or physician visits (other than routine check-ups). The subject memory aid will be reviewed with the subject at subsequent clinic visits and phone calls as needed.

Symptoms will be graded using the following scale:

- Grade 0: Not present
- Grade 1: Mild (present but easily tolerated)

- Grade 2: Moderate (able to tolerate routine activity with effort)
- Grade 3: Severe (unable to continue routine activity)

This information will be reviewed by study staff during follow-up subject contacts.

In the event a subject experiences an adverse event or injection site reaction that is still present at the end of the subject's participation in the study, the subject must be followed until resolution or until the event or abnormality resolves to the investigator's and/or sponsor's satisfaction. Follow-up procedures, evaluations, and outcomes will be recorded on the subject's data collection forms.

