Appendix B: Toxicity Table

ABBREVIATIONS: Abbreviations utilized in the Table:

ULN = Upper Limit of Normal	LLN = Lower Limit of Normal
Rx = Therapy	Req = Required
Mod = Moderate	IV = Intravenous
ADL = Activities of Daily Living	Dec = Decreased

NOTE: For any of the lab values listed below, if the Grade 1 value conflicts with the LLN value, the LLN value takes precedence and the event will not be considered a Grade 1 Adverse Event.

When the site-specific laboratory normal range is available, if there is a discrepancy between the laboratory value in the Appendix and the site specific laboratory normal range, the site normal range will take precedence in determining Grade 1 Adverse Events.

ESTIMATING SEVERITY GRADE

For abnormalities NOT found elsewhere in the Toxicity Tables use the scale below to estimate grade of severity:

- GRADE 1: **Mild** (events require minimal or no treatment and do not interfere with the subject's daily activities.)
- GRADE 2: **Moderate** (events result in a low level of inconvenience or concern with the therapeutic measures. Moderate events may cause some interference with functioning)
- GRADE 3: **Severe** (events interrupt a subject's usual daily activity and may require systemic drug therapy or other treatment. Severe events are usually incapacitating.)
- GRADE 4: Life-threatening (Any adverse drug experience that places the subject or subject, in the view of the investigator, at immediate risk of death from the reaction as it occurred, i.e., it does not include a reaction that had it occurred in a more severe form, might have caused death).

SERIOUS OR LIFE-THREATENING AEs

ANY clinical event deemed by the clinician to be serious or life-threatening should be considered a grade 4 event. Clinical events considered to be serious or life-threatening include, but are not limited to: seizures, coma, tetany, diabetic ketoacidosis, disseminated intravascular coagulation, diffuse petechiae, paralysis, acute psychosis, severe depression.

HEMATOLOGY				
	Grade 1	Grade 2	Grade 3	Grade 4
Hemoglobin (g/dl)				
Male:	11.0-12.4	9.6-10.9	8.3-9.5	<8.3
Female:	9.6-10.8	8.4-9.5	7.2-8.3	<7.2
Platelets (per cumm)	84,500-117,000	65,000-84,499	25,000-64,999	< 25,000
WBCs (thou/mcl)				
Lower Limit	2.5-2.9	1.9-2.4	1.0-1.8	<1.0
Upper Limit	11.9-15.1	15.2-21.6	21.7-25.0	>25

CHEMISTRIES	CHEMISTRIES				
	Grade 1	Grade 2	Grade 3	Grade 4	

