CARDIOVASC	CARDIOVASCULAR cont.				
	Grade 1	Grade 2	Grade 3	Grade 4	
Hypertension	Asymptomatic transient (<24 hrs) increase >20 mmHg in diastolic or to >140/90 and ≤150/95 mmHg; no treatment	recurrent or persistent (>24 hrs) or symptomatic increase >20 mmHg in diastolic or to >151/96 and ≤155/100 mmHg; monotherapy may be indicated	requiring more than one drug or more intensive therapy than previously or to >155/100 mmHg	Life-threatening consequences (e.g. hypertensive crisis)	
Hypotension	non applicable	Symptomatic corrected with oral fluids	Symptomatic IV fluids indicated	Shock–requiring use of vasopressors or mechanical assistance to maintain blood pressure	
Pericarditis	minimal effusion	mild/moderate asymptomatic effusion, no treatment	symptomatic effusion; pain; EKG changes	tamponade; pericardiocentesis or surgery required	
Hemorrhage, Blood Loss	microscopic/occult	mild, no transfusion	gross blood loss; 1-2 units transfused	massive blood loss; >3 units transfused	

SKIN				
	Grade 1	Grade 2	Grade 3	Grade 4
Mucocutaneous	erythema; pruritus	diffuse, maculo papular rash, dry desquamation	vesiculation or moist desquamation or ulceration	exfoliative dermatitis, mucous membrane involvement or erythema, multiforme or suspected Stevens- Johnson or necrosis requiring surgery
Induration	<25mm	25 - 50 mm	>50mm	
Erythema	<25mm	25 - 50 mm	>50mm	
Edema	<25mm	25 - 50 mm	>50mm	
Rash at Injection Site	<25mm	25 - 50 mm	>50mm	
Regional lymphadenopathy	Soft/spongy	Firm	Hard	

SKIN cont.				
	Grade 1	Grade 2	Grade 3	Grade 4
Pruritus	slight itching at injection site	moderate itching at injection extremity	itching over entire body	

SYSTEMIC	SYSTEMIC												
	Grade 1	Grade 2	Grade 3	Grade 4									
Allergic Reaction	pruritus without rash	localized urticaria	generalized urticaria; angioedema	Anaphylaxis									
Fever: oral	38.0 – 39.0 °C 100.4 F - 102.2 °F	>39.0 – 40.0 °C 102.3F - 104.0 °F	>40.0 °C >104.0 °F										

MUSCULOS	MUSCULOSKELETAL											
	Grade 1	Grade 2	Grade 3	Grade 4								
Arthritis	mild pain with inflammation, erythema or joint swelling – but not interfering with function	moderate pain with inflammation, erythema or joint swelling – interfering with function, but not with activities of daily living	severe pain with inflammation, erythema or joint swelling – and interfering with activities of daily living	permanent and/or disabling joint destruction								

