 - 1-5 years prior to enrollment
 - -1-12 months prior to enrollment
 - -Within 1 month of enrollment
 - -During Study
 - -If Ongoing at the end of the study, display "Ongoing" in the "Condition End Day" column.
 - -If ending is unknown at the end of the study, display "Unknown" in the "Condition End Day" column.

Listing 8 Compliance Data- All Vaccinated Subjects

Actual Treatment Group	Randomized Treatment Group	HCV Status	Subject ID	Dose 1 Study Day	Dose 1 Time	Dose 1 Administration Site	Dose 2 Study Day	Dose 2 Time	Dose 2 Administration Site	Missed Doses
Vaccine/Placebo	Vaccine/Placebo	Infected/Uninfected	xxxxxx	xx	xx:xxx	Left Arm/Right Arm	xx	xx:xxx	Left Arm/Right Arm	Dose 1/Dose 2

Implementation Notes:

- Sort order is Actual Treatment Group, Subject ID.
- If Dose 1 or Dose 2 is missed, list which dose in “Missed Doses” column if no doses are missed populate cell with “N/A”

Listing 9 Solicited Events – Systemic Symptoms—Safety Population

Vaccination	Study Day	Pre/Post Vaccination Day	Oral Temperature	Headache	Malaise	Myalgia/Body Ache	Nausea	Vomiting	Chills	Abdominal Pain	Arthralgia/Joint Pain
Actual Treatment Group: , Randomized Treatment Group: , HCV Status: , Subject ID:											
1	xxx	Pre-Vac	xxxx (Grade)	xxxx	xxxx	xxxx	xxxx	xxxx	xxxx	xxxx	xxxx
1	xxx	30 Min Post-Vac	xxxx (Grade)	xxxx	xxxx	xxxx	xxxx	xxxx	xxxx	xxxx	xxxx
1	xxx	Day 0	xxxx(Grade)	xxxx	xxxx	xxxx	xxxx	xxxx	xxxx	xxxx	xxxx
1	xxx	Day 1	xxxx(Grade)	xxxx	xxxx	xxxx	xxxx	xxxx	xxxx	xxxx	xxxx
1	xxx	Day 2	xxxx(Grade)	xxxx	xxxx	xxxx	xxxx	xxxx	xxxx	xxxx	xxxx
1	xxx	Day 3	xxxx(Grade)	xxxx	xxxx	xxxx	xxxx	xxxx	xxxx	xxxx	xxxx
1	xxx	Day 4	xxxx(Grade)	xxxx	xxxx	xxxx	xxxx	xxxx	xxxx	xxxx	xxxx
1	xxx	Day 5	xxxx(Grade)	xxxx	xxxx	xxxx	xxxx	xxxx	xxxx	xxxx	xxxx
1	xxx	Day 6	xxxx(Grade)	xxxx	xxxx	xxxx	xxxx	xxxx	xxxx	xxxx	xxxx
1	xxx	Day 7	xxxx(Grade)	xxxx	xxxx	xxxx	xxxx	xxxx	xxxx	xxxx	xxxx

Listing 10 Solicited Events – Local Symptoms—Safety Population

Vaccination	Study Day	Pre/Post Vaccination Day	Pain	Tenderness	Warmth	Erythema (Length)	Erythema (Functional Grade)	Induration (Length)	Induration (Functional Grade)
Actual Treatment Group: , Randomized Treatment Group: , HCV Status: , Subject ID:									
x	xxx	30 Min Post-Vac	xxxx	xxxx	xxxx	x	xxxx	x	xxxx
x	xxx	Day 0	xxxx	xxxx	xxxx	x	xxxx	x	xxxx
x	xxx	Day 1	xxxx	xxxx	xxxx	x	xxxx	x	xxxx
x	xxx	Day 2	xxxx	xxxx	xxxx	x	xxxx	x	xxxx
x	xxx	Day 3	xxxx	xxxx	xxxx	x	xxxx	x	xxxx
x	xxx	Day 4	xxxx	xxxx	xxxx	x	xxxx	x	xxxx
x	xxx	Day 5	xxxx	xxxx	xxxx	x	xxxx	x	xxxx

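### SAP 4.5 grades solicited reactions only on the functional scale of protocol 9.4.4, so the Appendix B Grade 3 cut-offs for erythema, induration and fever have no defined role in the primary safety endpoint

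*SAP*

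**What the plan says.** Severe solicited reactions on Days 0-7 after each dose are one of the primary safety endpoints (protocol 3.1.1, SAP 3.2). SAP 9.3.1 takes each subject's worst grade, splits it into Grade 3 against everything lower, and compares the arms with Fisher's exact test (Tables 44-46).

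For the grade itself, SAP 4.5 says: "Solicited reactogenicity symptoms will be graded using the scale in section 9.4.4 of the protocol". In protocol 9.4.4 the top category is "Grade 3: Severe (unable to continue routine activity". The same section says "Erythema and induration at the vaccination site will be measured in millimeters" and has subjects record temperature, but it converts neither measurement into a grade.

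Protocol 9.4.2 says: "Event severity will be graded according to parameters shown in Appendix B". Its own verbal definitions apply only to what the tables do not cover. Appendix B restricts its generic scale in the same way: "For abnormalities NOT found elsewhere in the Toxicity Tables use the scale below to estimate grade of severity". Erythema is covered: "Erythema <25mm 25 - 50 mm >50mm" for Grades 1 to 3. Induration has the same cut-offs, and oral fever is Grade 3 above 40.0 C.

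The SAP cites Appendix B for unsolicited events and laboratory values only, and its reproduced grading tables (124-127) contain no skin or fever rows. It does say "Erythema and induration at the vaccination site will be measured in millimeters and functional grade". Listing 10 accordingly has a length column and a separate column, "Erythema (Functional Grade"), with the same pair for induration. Listing 9 prints a grade beside oral temperature.

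**The concern.** Three of the fourteen solicited items (erythema, induration and fever) are measured rather than felt. For these, the documents either define *severe* in two ways or do not say how to get from the measurement to a grade. The tables need a single severity per item. Tables 47-52, for example, have one none-to-severe block each for erythema, induration and elevated oral temperature. Two programmers following the SAP faithfully could build different tables.

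What is at stake is a primary safety endpoint. Under the only scale that the SAP names, a sign that Appendix B calls Grade 3 can drop out of the severe count. If the rule is left open, it could be settled after the results by arm have been seen.

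**Working it through.** No sample size, power or alpha figure in the plan depends on the grading scale, so there is no stated figure to reproduce. The check is a comparison of texts, followed by one illustration.

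**1. The same finding under each rule**

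| Finding in a subject who keeps up routine activity | Protocol 9.4.4 (named by SAP 4.5) | Protocol 9.4.2 with Appendix B |
|---|---|---|
| Erythema 60 mm | not Grade 3 | Grade 3 (above 50 mm) |
| Induration 60 mm | not Grade 3 | Grade 3 (above 50 mm) |
| Oral temperature 40.5 C | no rule for grading a temperature | Grade 3 (above 40.0 C) |

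Erythema and induration feed Tables 44 (any) and 45 (local). Fever feeds Tables 44 and 46 (systemic).

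**2. Direction for erythema and induration**

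Let F be the subjects with a functional Grade 3 on any item of the composite, and M those with erythema or induration above 50 mm.

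- Functional-only count = |F|.
- Higher-of-two count = |F or M| = |F| + |M but not F|.

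The second is never smaller than the first. The gap is the number of subjects who are Grade 3 by size and not severe through any other symptom; subjects already severe through pain or malaise add nothing to it. Against a millimetre-only rule no direction follows: a 20 mm reaction that stops activity is Grade 3 by function and Grade 1 by size.

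**3. Size**

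The gap needs the rate of |M but not F| in each arm, and the documents do not give one. In HCV003 (protocol 2.2.3), 67% of nine MVA-NSmut recipients had erythema and 56% swelling or induration, but of any size. In the same study 74% of local reactions were mild and 4% severe. In HCV001, 93% of local reactions were mild. None of these figures says how often a reaction exceeds 50 mm without limiting activity.

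**4. Sensitivity of the test (illustration with assumed counts)**

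Take 270 per arm (SAP 5) and suppose no severe reactions on placebo. For k severe on vaccine, the two-sided Fisher p is 2 x C(270,k) / C(540,k).

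- k = 5: 2 x (270 x 269 x 268 x 267 x 266) / (540 x 539 x 538 x 537 x 536) = 0.061.
- k = 6: multiply by a further 265/535, giving 0.030.

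With counts this low, reclassifying one subject can move p across 0.05. This shows that the rule should be fixed in advance. It does not estimate what will happen in the trial.

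**The case against.** The strongest reply is that the SAP does what the protocol tells it to do. Protocol 9.4.4 is the section on reactogenicity; it names fever, erythema and induration and then gives the functional scale. Section 9.4.2 is the general rule for event severity, and letting the specific section govern is a fair reading. This stands: a reader might infer that the SAP has departed from the protocol, and it has not. It does not remove the problem, because Appendix B has millimetre rows for injection-site signs, and if 9.4.4 overrides them the lengths collected never reach the endpoint.

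A second reply is that the SAP nowhere says that only the functional grade counts. That is correct: it is silent on how the two values combine. The functional-only result is the literal reading, not a stated exclusion of the measurement.

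A third concerns fever. A reader might infer that a 40.5 C fever would be scored Grade 1 or 2. The documents do not show that. The grade beside temperature in Listing 9 and the table label for elevated oral temperature suggest grading by value, and Appendix B holds the only cut-offs available. Fever is undefined rather than shown to be misgraded.

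Finally, lengths and functional grades are both listed by subject and day, so a large reaction stays visible in the listings. That helps a careful reader but does not define the tabulated endpoint.

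**Conclusion.** The point holds as a gap in definition that the SAP inherits from a conflict inside the protocol. It is clearest for erythema and induration, where a Grade 3 sign under Appendix B can be left out of Tables 44-46. For fever, the grading rule is missing.

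The size is unknown and may be small. A reader might infer that the vaccine-placebo comparison is biased towards no difference, or that the choice of scale will decide the primary safety test. With a saline placebo, any lost reactions would be expected mainly on vaccine, but the documents give neither the exceedance rate nor its overlap with other severe symptoms, so neither inference is established. Protocol 11.1 also treats testing as a supplement to description. The only firm statement on direction is that functional-only grading cannot give a higher severe count than the higher-of-two rule.

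The scope is Tables 44-56 and Figures 19-26, which use severity. Tables 41-43 count any event and Table 57 compares none with mild or greater, so neither uses *severe*. The trigger in protocol 9.6 for Grade 3 solicited systemic reactions can be affected through fever only, since erythema and induration are local.

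**What to change.** Before unblinding, add to SAP 4.5 and 9.3.1 that, for analysis:

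- fever is graded from the recorded temperature by the Appendix B cut-offs;
- erythema and induration take the higher of the Appendix B millimetre grade and the functional grade wherever maximum severity or *severe* is derived (Tables 44-56, Figures 19-26);
- subjective symptoms stay on the 9.4.4 scale.

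The cost is wording and programming. Temperature, length and functional grade are already collected. The downside is that the reported severe rate may come out slightly higher.

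Separately, protocol 9.4.2, 9.4.4 and Appendix B contradict each other on these signs and must be reconciled, including for the fever grade that feeds the 9.6 trigger. Which rule should govern halting is not judged here.

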5. SAMPLE SIZE CONSIDERATIONS

Sample size calculations are based on the assumption of detecting a 60% reduction in incidence of chronic infection over 18 months of post-vaccination follow-up among vaccinated subjects compared to unvaccinated controls in an according to protocol (ATP) analysis. A total of 43 observed events of chronic infection in the ATP cohort would provide power of 85% for a two-sided log rank test conducted at the significance level (alpha) of 0.05 to detect a 60% reduction in hazard rate. The incidence of chronic infection among controls is assumed to be 14% annually [10]. Assuming 14 cases/100 person-years (PY) in the control group, and 5.6 cases/100 PY in the vaccine group, a total of 292.5 subjects in the ATP cohort followed for 1.5 years would provide on average 43 events. We further assume that 65% of enrolled subjects will be retained in the ATP cohort. Therefore, we inflate the required number of subjects by a factor of $1/0.65$ and obtain a target enrollment of 540 subjects, or 270 subjects per vaccination group.

The original enrollment target of the study was 344 subjects. At the April 29, 2014 DSMB meeting, the DSMB reviewed the progress towards the goal of 43 observed events of chronic infection in the ATP cohort and recommended increasing the target enrollment from 344 to 450, or 225 subjects per vaccination group.

At the September 2, 2015 DSMB meeting, the DSMB reviewed the progress towards the goal of 43 observed events of chronic infection in the ATP cohort and recommended increasing the target enrollment from 450 to 540 subjects, or 270 subjects per vaccination group.

6. GENERAL STATISTICAL CONSIDERATIONS

6.1. General Principles

Tabulations will be used extensively to summarize the data. Unless otherwise specified, all continuous variables will be summarized using the following descriptive statistics: n (number of non-missing observations for the measure being summarized in the specified analysis population), mean, standard deviation, median, maximum and minimum. Immunogenicity summaries will use geometric mean. The frequency and percentages (based on the sample size for the specified analysis population and treatment group, N) of observed levels will be reported for all categorical measures. Wilson confidence intervals for binomial proportions and differences in binomial proportions will be computed for efficacy variables. Blaker confidence intervals for binomial proportions and differences in binomial proportions will be computed for safety variables. In general, all data will be listed by treatment group and/or subject, and when appropriate by visit number within subject.

All summary tables will be structured with a column/sub-table for each treatment group (Vaccine, Placebo, and All Subjects). The total population size (N) relevant to that table/column if applicable, including any missing observations will be displayed in the tables.

Note that in the data listings, Subject ID is the unique subject identifier, not the Study ID used on study and dates will not be included, only Study Day.

6.1.1. Pseudo Code

The following SAS® pseudo code will be used to calculate the following for safety analyses:

Chi-Square test at 5% two-sided significance level:

```
proc freq;
    Table treatment*analysis_variable / chisq;
    ods output ChiSq=outputdsn;
run;
```

Fisher's Exact test at 5% two-sided significance level:

```
proc freq;
    Table treatment*analysis_variable / exact;
    ods output FishersExact=outputdsn;
run;
```

95% Wilson CI for proportions/percents:

```
Proc freq;
    Table treatment*analysisvariable / binomial(wilson);
    ods output binomialcls=outputdsn;
Run;
```

95% Wilson CI for difference in proportions (produces Newcombe CI):

```
Proc freq;
    Table treatment*analysisvariable / riskdiff(cl=Wilson);
    Exact Riskdiff;
    ods output pdiffcls=outputdsn;
Run;
```

95% Exact Blaker CI for proportions/percents:

```
Proc freq;
  Table treatment*analysisvariable / binomial(blaker);
  ods output binomialcls=outputdsn;
Run;
```

Odds ratios using ordinal logistic regression:

```
PROC LOGISTIC data=dataset;
  Class treatment (ref='Placebo') baseline(ref='None') / param=reference;
  Model severity_postvaca1=baseline treatment;
Run;
```

```
PROC LOGISTIC data=dataset;
  Class treatment (ref='Placebo') baseline(ref='None') / param=reference;
  Model severity_postvac2=baseline treatment;
Run;
```

See Section 8 for pseudocode to be used in the efficacy analyses.

